#### 3. PURPOSE AND SCOPE

This document is based on the final protocol (Version 1.0/21-Oct-2020) of BI Study Number 1160-0304 that have been approved by Institutional Review Board (IRB). This document is intended to provide comprehensive details on all statistical programming specifications and statistical methodology for analysis of BI Study Number 1160-0304. This document also provided anticipated data transformations, manipulations, coding, and other details of the analysis not provided in the study protocol. A detailed description of the planned table and figures presented in the clinical study report (CSR) is provided in the mock-up tables documents. This SAP only covers the planned analysis of all safety and efficacy data collected on paper (source documents) and captured in case report forms (CRFs).

This document is written with consideration of the recommendations outlined in the International Conference on Harmonisation (ICH) E9 guideline entitled, "Guidance for Industry: Statistical Principles for Clinical Trials" and the ICH E3 guideline entitled, "Guidance for Industry: Structure and Content of Clinical Study Reports".

Statistical Analysis Plan (SAP) for Non-Interventional Studies (NIS) BI Study Number 1160-0304

Page 6 of 27

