#### 6. RESEARCH METHODS

#### 6.1 STUDY DESIGN

This is a multi-center, 1:1 randomized study to evaluate the effects of educational intervention on adherence to dabigatran, for up to 12 months. The study will be carried out at around 20 hospitals ( $20 \pm 3$ ), where AF patients are mainly treated in Taiwan. A total of 1,200 patients are planned to be enrolled to target 1,000 patients included in the analysis.

Patients newly diagnosed with AF within 1 month, under 75 years old, and newly prescribed with dabigatran on physician's decision per local labelling will be enrolled and equally randomized to receive standard of care (routine clinical practice) or standard of care (routine clinical practice) with advanced educational intervention. To create the randomization numbers, we will use block randomization by Statistical Analysis Software (SAS®) Version 9.4 or higher (SAS Institute, Cary, NC, USA).

The study duration consists of a 1-year enrolment period and a 12-month follow-up period consisting of visits at 3, 6, 9, and 12 months for each individual patient. Being an NIS, the time points of follow-up visits are set in accordance with the routine outpatient follow-ups of AF management in Taiwan. Patients will be continuously followed until death, lost to follow-up, or end of data collection at 12 months, whichever comes first.

The educational materials from "Shared decision making of treatment of NOAC in AF patients" (NTA: 180647) and "Atrial Fibrillation Patient Care in Hospitals" (NTA: 190707) will be used as the educational materials for the experimental group. The education materials will be delivered after randomization (baseline); and at 3, 6, and 9 months thereafter. The adherence to dabigatran will be measured by MMAS-8 score at 3, 6, 9, and 12 months.

The comorbidities, VASc score, and HAS-BLED score will be recorded at baseline; and at 3, 6, 9, and 12 months. Stroke, thromboembolic events, and bleeding-related events will also be captured during 12 months of follow-up.

The whole NIS will be implemented by a Contract Research Organization (CRO) under Local Boehringer Ingelheim's governance.

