#### **Inclusion criteria**

Patients can be included if ALL the following criteria are met:

- (1) Provide written informed consent prior to participation
- (2) Female or male patients aged  $\geq$  20 years and < 75 years, newly diagnosed with non-valvular atrial fibrillation (NVAF) within 1 month and has newly prescribed with dabigatran on physician's decision before study enrolment.

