#### 7. VARIABLES

#### 7.1.1 Exposures

Being an NIS, the prescription of dabigatran will be in accordance with the Summary of Product characteristics and physician's discretion. Treatment record of dabigatran will be collected and recorded on CRF across the 12 months of study period. Data to be collected include start/end date of administration, dose, and the reason for dose adjustment or interruption.

Mean daily dose of dabigatran will be summarize by study group. If dabigatran treatment recorded in CRF had discontinued (that's the end date of administration had been recorded), the dabigatran treatment duration will be the time range of start/end date of administration. However, if dabigatran treatment recorded in CRF is ongoing, the dabigatran treatment duration will be the time range of start date of administration to the date of last dabigatran treated.

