#### 10. DATA ANALYSIS

The main and further analysis population will consist of all eligible patients (i.e., all patients who have signed the informed consent and have fulfilled all eligibility criteria).

Continuous variables will be reported as number, mean, standard deviation (SD), minimum, maximum, and 95% confidence interval (CI). Categorical variables will be summarized as number and frequency or percentage with observed (non-missing) data. Missing numbers of both continuous and categorical variables will also be summarized.

As for comparisons of continuous data between baseline and follow-up visit, paired-t test will be performed at the significant level of 0.05. Shapiro—Wilk test will be performed to test the normality of data. When normality assumption is violated, Wilcoxon signed-rank test will be performed instead. On the other hand, McNemar's test will be performed to for comparisons of categorical data between baseline and follow-up visit at the significant level of 0.05.

For the endpoints pre-identified to compare between patients with and without advanced educational intervention, the analyses will be done by independent t-test for continuous data at the significant level of 0.05. Shapiro–Wilk test will be performed to test the normality of data. When normality assumption is violated, Wilcoxon rank-sum test will be performed instead. On the other hand, Chi-square or Fisher's exact test will be performed to for comparisons of categorical data at the significant level of 0.05.

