#### 10.1 Main analysis

The primary outcome is to describe the proportion of patients with high adherence to dabigatran treatment which is defined as achieving MMAS-8 score of 8 points at 12 months for each group.

• The proportion of patients with high (MMAS-8 score: 8 points) adherence to dabigatran treatment at x months ( $P_{H,x}$ ) is defined as following formula:

$$P_{H,x} = \frac{\text{Number of subjects with 8 points of MMAS} - 8 \text{ score at x months}}{\text{Number of subjects at x months}}$$

Subjects without MMAS-8 value recorded at 12 months will be excluded from the analysis of primary endpoint. The Chi-square test or Fisher's exact test will be used to test the equality between two study groups.

The secondary analyses are described below:

- (1) The proportion of patients with high (MMAS-8 score: 8 points) adherence to dabigatran treatment at each visit (3, 6, and 9 months),
- (2) The proportion of patients with medium (MMAS-8 score: 6-7 points) and low (MMAS-8 score < 6 points) adherence to dabigatran treatment at each visit (3, 6, 9 and 12 months),
- (3) The mean MMAS-8 score at each visit (3, 6, 9 and 12 months) and
- (4) The discontinuation rate of dabigatran and reasons for discontinuation (switch or stop treating dabigatran).

Similar as primary endpoint, Chi-square test or Fisher's exact test will be used to test the equality of MMAS-8 score, discontinuation rate and reasons for discontinuation between two

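### The visible text of SAP 10.1 compares dabigatran discontinuation as a crude proportion without saying how patients who leave with no recorded stop are counted

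*SAP*

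**What the plan says.** Discontinuation of dabigatran, with its reasons, is the fourth secondary outcome. SAP 10.1 likens its analysis to that of the primary endpoint and applies chi-square or Fisher's exact tests to "test the equality of MMAS-8 score, discontinuation rate and reasons for discontinuation between two" study groups. A formula and an exclusion rule are given for the MMAS-8 proportion, but none is visible for discontinuation.

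Other rules bear on the count:

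- SAP 10, population: "The main and further analysis population will consist of all eligible patients".
- SAP 10, percentages: "Categorical variables will be summarized as number and frequency or percentage with observed (non-missing) data".
- SAP 7.1.1, written for treatment duration, treats dabigatran as discontinued if "the end date of administration had been recorded". If treatment is ongoing, "the dabigatran treatment duration will be the time range of start date of administration to the date of last dabigatran treated".
- SAP 6.1, follow-up: "Patients will be continuously followed until death, lost to follow-up, or end of data collection at 12 months, whichever comes first".
- Protocol 9.7.3 seeks no further information after withdrawal, and SAP 9.2 rules out imputation.

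Protocol 9.7.1 planned this outcome as descriptive; the SAP adds the test. SAP 3 says the detailed description of the tables "is provided in the mock-up tables documents", which are not part of the public documents.

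**The concern.** Take a patient who leaves at month 4 still recorded as on dabigatran. Under SAP 7.1.1 that patient looks ongoing, so not discontinued. Under the observed-data rule in SAP 10 the 12-month status is unknown, and the patient leaves the denominator. If the primary endpoint's exclusion is carried over, only patients assessed at 12 months count. In the third case, stops recorded in patients who later left are dropped as well.

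Two programmers following the text could report different rates, while SAP 11 requires their results to be identical. Because the protocol planned a description, the estimate matters more than the test. It is also the only listed primary or secondary outcome that does not come from the self-reported MMAS-8.

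**Working it through.** **Inputs from the documents.** 1,200 enrolled, 20% drop-out and 1,000 completing (Protocol 9.5); 1:1 allocation, so 600 per arm (SAP 6.1); level 0.05 (SAP 10), taken as two-sided.

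**Assumptions.** The documents give no discontinuation rate and no drop-out by arm. I take true 12-month rates p of 10% to 40%, constant hazards and, at first, drop-out d independent of stopping.

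**The plan's own figure.** 1,200 × (1 − 0.20) = 960, not 1,000. The stated 1,000 of 1,200 implies 1 − 1,000/1,200 = 16.7% drop-out. Both values are used below.

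**Formulas.** a = −ln(1 − p), b = −ln(1 − d), s = a + b. Recorded stops R = (a/s)(1 − e^−s). Leavers without a stop V = (b/s)(1 − e^−s).

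**At p = 0.30, d = 0.20.** a = 0.3567, b = 0.2231, s = 0.5798, and 1 − e^−s = 1 − 0.70 × 0.80 = 0.44. So R = 0.2707 and V = 0.1693, which is about 203 of 1,200.

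- Leavers counted as ongoing: R = 27.1%.
- Leavers without a stop removed: R/(1 − V) = 0.2707/0.8307 = 32.6%.
- Completers only: p(1 − d)/(1 − d) = 0.24/0.80 = 30.0%. This discards 0.2707 − 0.24 = 3.1% of patients (about 37 of 1,200) whose stop was recorded before they left.

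| True rate | Drop-out | Leavers ongoing | Leavers removed | Completers only |
|---|---|---|---|---|
| 10% | 20% | 9.0% | 11.1% | 10.0% |
| 20% | 20% | 18.0% | 22.0% | 20.0% |
| 30% | 20% | 27.1% | 32.6% | 30.0% |
| 40% | 20% | 36.2% | 43.0% | 40.0% |
| 30% | 16.7% | 27.6% | 32.1% | 30.0% |

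**Between-arm test, no true difference, true rate 30%.** The rejection rate is Φ((|δ| − 1.96·SE0)/SE1) + Φ((−|δ| − 1.96·SE0)/SE1). Here δ is the spurious difference (lower minus higher drop-out arm), and SE0 and SE1 are the pooled and unpooled standard errors.

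| Drop-out by arm | Leavers ongoing: δ, type I error | Leavers removed: δ, type I error |
|---|---|---|
| 20% vs 20% | 0; 5.0% | 0; 5.0% |
| 17.5% vs 22.5% | +0.76 points; 6.0% | −0.75 points; 5.7% |
| 15% vs 25% | +1.53 points; 9.2% | −1.51 points; 8.0% |

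The two readings err in opposite directions.

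**Drop-out linked to stopping.** Simulation with 2,000,000 draws, total drop-out held at 20% and a true rate of 30%. With leaving 2 or 4 times as likely after a stop, completers-only gives about 28% and 25%. Kaplan-Meier gives about 30.0% throughout, provided every stop is recorded.

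**Stops unrecorded.** If half of later leavers' stops are never recorded, the results for a leaving hazard ×1, ×2 and ×4 after a stop are (to about 0.1 point):

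- Kaplan-Meier: 28.5, 27.6, 26.4%.
- Leavers counted as ongoing: 25.5, 24.9, 24.1%.
- Leavers removed: 31.3, 30.2, 28.7%.

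**The case against.** A reader might infer that any crude proportion misstates the 12-month rate. The documents do not support that. SAP 10.1 likens this analysis to the primary endpoint, which leads naturally to completers only, and that is unbiased when drop-out is independent of stopping. It still discards recorded stops and fails if patients who stop tend to leave.

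A reader might also infer that a time-to-event estimate is always closer. When half of later leavers' stops go unrecorded, Kaplan-Meier is off by 1.5, 2.4 and 3.6 points, against 1.3, 0.2 and 1.3 for the leavers-removed proportion. That proportion does better only because its two errors partly cancel, which cannot be planned for, but the comparison stands. Log-rank also adds little power when drop-out is equal: 85.7% against 84.3% and 84.6% for an assumed 22% versus 30%.

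The effect is small against sampling error. At 30% with 600 per arm, the 95% half-width is 1.96 × √(0.3 × 0.7/600) = 3.7 points per arm and 5.2 points for the difference. This is fair, although sampling error is reported in a confidence interval and this bias would not be.

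It can be argued that SAP 7.1.1 with the all-eligible population already settles the count. It may be what was meant, but that rule is written for treatment duration, and it is the reading that understates the rate.

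Finally, it would go too far to say that no definition exists. The mock-up tables were not available. SAP page 18, after the secondary outcomes, shows no text in this copy, and page 25, within 10.1, shows very little.

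**Conclusion.** The concern holds for the visible text. Discontinuation is compared as a crude proportion whose handling of leavers is undefined, and the surrounding rules point to three different counts. At an assumed true 30% with 20% independent drop-out, these span 27.1% to 32.6%. Two of the three are biased even when leaving has nothing to do with stopping; the third is biased when it does.

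A reader might infer that the randomised comparison is compromised. That does not follow. Type I error stays near 5% with equal drop-out. It reaches about 8-9% under the first two readings only if drop-out is as unequal as 15% versus 25%, and the documents give no drop-out by arm. The outcome is secondary and the primary result is untouched. The point is worth correcting, but its importance is modest. The sizes rest on assumed discontinuation rates and constant hazards.

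**What to change.** In SAP 10.1, define the endpoint as the 12-month cumulative incidence of dabigatran stop or switch by randomised arm, and report the between-arm difference with a 95% CI.

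- Count time from randomisation, since dabigatran is prescribed on the physician's "decision before study enrolment".
- Censor leavers at the last contact at which they were known to be on dabigatran, and treat death as a competing event.
- State which recorded end dates count as a stop for this endpoint, because SAP 7.1.1 also collects interruptions.
- If a test is kept, use log-rank in place of chi-square. Show reasons descriptively by arm.
- Add a sensitivity analysis counting leavers as discontinued. In the worked case this is R + V = 0.2707 + 0.1693 = 44.0%, an upper bound.

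The main estimate assumes non-informative drop-out and is low if stops before leaving go unrecorded, so the SAP should say so. If the crude proportion is kept, one sentence must give its numerator, its denominator and how leavers count. That removes the ambiguity but not the bias of the reading chosen.

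The cost is SAP wording and standard SAS survival procedures. No new data are needed: SAP 7.1.1 already uses start and end dates and the date last treated, and Protocol 9.10.2.1 lists visit and prescription dates. If the table shells already define the rate, carry that definition into the SAP and check it against these points.

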# Statistical Analysis Plan (SAP) for Non-Interventional Studies (NIS) BI Study Number 1160-0304

Page 25 of 27

study groups. Lastly, the mean MMAS-8 score between two study groups will be test by Independent t test or Wilcoxon rank-sum test.

Statistical Analysis Plan (SAP) for Non-Interventional Studies (NIS) BI Study Number 1160-0304

Page 26 of 27

### 11. QUALITY CONTROL

The quality control details for study data is referred to study protocol section 9.8.

As for statistical results, responsible biostatistician in current study should stick to all the statistical programming specifications and statistical methodology described in the current document.

Last but not least, designated CRO will assigned an independent biostatistician as double programmer for current study. All statistical results generated by responsible biostatistician need to be the same as those generated by double programmer to ensure the reliability and correction of statistical results.

- 12. REFERENCES
- 12.1 PUBLISHED REFERENCES

None.

12.2 UNPUBLISHED REFERENCES

None.

ANNEX 1. ADDITIONAL INFORMATION

None.

